Study Endpoints	
Primary Endpoint: Number of VRP-Clinic neck movements that the evaluator recognizes as useful for rehabilitation. Success acceptance criteria defined as: 80%
 
Secondary Endpoint: Safety – Record of any adverse event occurring during the study. All AEs will be recorded and evaluated as part of the risk management for the device

	Study Protocol			
	VRP-CLINIC SOFTWARE EVALUATION - IN SUPPORT OF REHABILITATION			
Protocol#	VRP02	Version #, Date.	Version 01 22-March-2017	Page 6 of 12

INTRODUCTION

One of the most common musculoskeletal dysfunctions in the population is dysfunction of the cervical spine reaching an annual prevalence of 30-50% in western societies and associated with considerable pain, disability, and costs [1, 2].

Physical therapies are first line treatments aimed at improving muscle strength and range of motion, often requiring considerable commitment by subjects over a long period of time [3] and frequently requiring a home exercise program for a successful outcome [4]. However, compliance to home exercises is not as high as desired therefore, it is imperative to include new motivational interventions to increase compliance.

Virtual reality (VR) technology has been used for several decades for a variety of psychosocial interventions. The use of VR was studied for a variety of rehabilitation conditions [5, 6]. Specifically, the effect of neck exercises using VR was previously tested on both asymptomatic individuals and patients with chronic neck pain and was shown to be useful in increasing cervical motion [7-9].

STUDY RATIONAL

In recent years, commercial and research groups have been studying the effect of VR systems on the rehabilitative progress and developing new platforms. As the variety of available products widens, each system focuses on specific hardware and different rehabilitation aspects. The software presented in the current study focuses on the rehabilitation of the upper body.

STUDY OBJECTIVES

The current study was designed to evaluate neck movements performed according to the VRP-Clinic software, and to verify that they promote physical activities that correspond with physical rehabilitation.

STUDY DEVICE

Indications for Use

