The session will be recorded with a video camera. Camera recording will start after the VR headset is placed on the subjects' head and terminate before removing it, to ensure the participants' privacy.

The video will be viewed and evaluated separately by 4 clinicians. The clinicians will identify each movement seen on the video from a predefined list and determine if such a movement is recommended as part of a rehabilitation training program for neck related pathologies.

Endpoints:

Primary Endpoint

Number of VRP-Clinic neck movements that the assessing clinician recognizes as rehabilitation movements.

Success acceptance criteria defined as: 80%

Secondary Endpoint:

Safety – Record of any adverse event occurring during the study.

All AE's will be recorded and evaluated as part of the risk management for the device

Study Duration

	Study Protocol			
	VRP-CLINIC SOFTWARE EVALUATION - IN SUPPORT OF REHABILITATION			
Protocol#	VRP02	Version #, Date.	Version 01 22-March-2017	Page 8 of 12

Duration of subject's participation: 30 minutes of which the actual exercise is expected to take not more than 5 minutes

Study duration: The total study duration from recruitment to final data collection is estimated to be four months

STUDY POPULATION AND SUBJECT SELECTION

Source and sample size

Twenty (n=20) healthy adult subjects will be included in this study. The subject will be recruited by the investigator by use of an IRB approved advertisement.

Eligibility

Each subject will be evaluated by the Investigator to assess his/ her suitability for entry into this study according to the following criteria:

Inclusion Criteria

Eligible subjects must meet all of the following inclusion criteria:

1. Healthy male or female
2. Age 18-65

Exclusion Criteria

Eligible subjects must not meet any of the following exclusion criteria:

1. History of neck related disorders (Whiplash, disc degeneration disease or other acute cervical spine conditions)
2. Current neck pain
3. Under medical treatment or observation for any health-related issue during the study
4. Recent trauma
5. Oncology background
6. Acute disease/illness
7. Pregnancy.
8. Using drugs that could potentially affect physical function and balance (such as corticosteroids, antipsychotics or antidepressants)
9. Vision problems that require glasses (not all frame types can fit into the headset)

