The investigator may withdraw a subject if, in his clinical judgment, it is in the best interest of the subject or if the subject cannot comply with the protocol. At the discretion of the investigator, these subjects may be replaced. Attempt should be made to complete any examinations.

Subject Termination

In case of dropout or subject removal the investigator will describe the reason for discontinuing the subject's participation in the Termination CRF.

Compensation

At the end of the session, subjects will receive a coupon for use at the local cafeteria for purchase of a hot drink and cake ("café u maafe") approximately worth 15 NIS as compensation for their time.

	Study Protocol			
	VRP-CLINIC SOFTWARE EVALUATION - IN SUPPORT OF REHABILITATION			
Protocol#	VRP02	Version #, Date.	Version 01 22-March-2017	Page 9 of 12

STUDY PROCEDURES

Screening

Eligibility: the volunteer will be screened to determine if he/she meets the study inclusion/exclusion criteria.

Informed consent Prior to the study visit, informed consent will be obtained. When the participant fully understands the procedure, possible benefits and risks of the study, the subject will be asked to sign and date the informed consent document.

Subject number If the subject meets the study inclusion/exclusion criteria, the subject will be assigned the next consecutive number.

Medical history and demographic information: Basic medical and demographic information will be collected including age, gender, height, weight, head circumference, general medical background and specific information related to head/neck.

Interventions and procedures:

Subject Preparation and Instructions

The subject will sit on a steady chair, with back support, in front of a desk where the device sensors are located. Once starting the training program, the subject will receive instructions appearing in the graphic VR environment:

Neck movements

The software will guide the subjects to perform neck movements.

EVALUATIONS

Physiotherapist Evaluation and Assessment of Videos

1. Identification of each movement seen in the video from the list detailed in "Neck Movement" section
2. Determining if the use of such movement is recommended for rehabilitation

Safety

All adverse events (AEs) will be documented and evaluated as part of the risk management for the device

	Study Protocol			
	VRP-CLINIC SOFTWARE EVALUATION - IN SUPPORT OF REHABILITATION			
Protocol#	VRP02	Version #, Date.	Version 01 22-March-2017	Page 10 of 12

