STATISTICAL CONSIDERATIONS AND ANALYSIS

Sample Size Justification

The rationale for the sample size is based on obtaining exact 95% confidence intervals for the activity movements which achieved 80% success. When the sample size is 20, a one-sided 95.0% confidence interval for a single proportion using the large sample normal approximation will extend at most 0.18 from the observed proportion.

Subject Accountability

A CONSORT flow diagram will be presented that will include the number of subjects screened and reasons for screening failures; the number of subjects, who were enrolled, as well as the reasons for all enrollment discontinuations grouped by major reason; A list of discontinued subjects, protocol deviations, and subjects excluded from the analyses.

Data Analysis

Descriptive statistics and summary tables will be provided giving sample size, absolute and relative frequency of categorical variables and sample size, arithmetic mean, standard deviation, median, minimum and maximum, percentiles and 95% CI (Confidence Interval) for means of continuous variables. All measured variables and derived parameters will be listed individually and, if appropriate, tabulated by descriptive statistics.

Study Hypothesis – Primary Endpoint:

The number and percentage of neck movements which achieve a success rate of at least 80% will be tabulated. Exact 95% binomial confidence intervals will be calculated for the rate of neck movements which achieve 80% success.

Safety - Secondary Endpoint

Adverse events will be coded according to coding dictionaries (MedDRA version 13.1 or higher) and presented in tables by system organ class, preferred term. The number and percentage of subjects who experienced any adverse events will be tabulated.

ADVERSE EVENTS

In this study, Serious Adverse Experience (SAE) is to be reported by the investigator within 24h to the IRB. The “Adverse Experience” CRF should be filled in all events of SAE and in other cases of Adverse Experience (AE) which, in the judgment of the investigator, affect this protocol.

Anticipated Side Effects

In this study, we are not anticipating any side effects.

Anticipated Adverse Effects/Risks

The movements not expected to cause any pain or discomfort.

	Study Protocol			
	VRP-CLINIC SOFTWARE EVALUATION - IN SUPPORT OF REHABILITATION			
Protocol#	VRP02	Version #, Date.	Version 01 22-March-2017	Page 11 of 12

MISCELLANEOUS

Ethical Considerations

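### The n=20 precision of 0.18 does not describe the usefulness endpoint, which rests on repeated judgements by the same four clinicians

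*Combined protocol and SAP*

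**What the plan says.** The synopsis (Study Endpoints) gives the primary endpoint as "Number of VRP-Clinic neck movements that the evaluator recognizes as useful for rehabilitation". The synopsis objectives put recognition of the movements first and usefulness second. The endpoint in the body of the protocol is worded differently again, as movements recognised as rehabilitation movements. In both places the threshold reads "Success acceptance criteria defined as: 80" (per cent).

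On the ratings, Study Design – Overview says "The video will be viewed and evaluated separately by 4 clinicians". The clinicians pick each movement from a predefined list and then "determine if such a movement is recommended as part of a rehabilitation training program for neck related pathologies". The Evaluations section repeats the second step: "Determining if the use of such movement is recommended for rehabilitation".

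On size and analysis, "Twenty (n=20) healthy adult subjects will be included in this study". The precision statement in Sample Size Justification opens "When the sample size is 20, a one-sided 95.0% confidence interval for a single proportion" and puts the limit no further than 0.18 from the estimate, by the normal approximation. Study Hypothesis – Primary Endpoint then states: "Exact 95% binomial confidence intervals will be calculated for the rate of neck movements which achieve 80% success". The plan gives no denominator for that interval, no rule for combining the four clinicians, and no allowance for repeated ratings by one clinician.

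**The concern.** A binomial interval needs independent trials. The usefulness question is put about a type of movement. A clinician who thinks that type belongs in neck rehabilitation may well give the same answer on many of the 20 videos. To that extent, more subjects inform recognition of the movements but add little on usefulness, where the number of clinicians limits the information.

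What is at stake is how the result is read. Unanimous approval by four people could be shown as 20/20 with a lower limit of 83.2%, above the 80% threshold. Four independent opinions, 4/4, have a lower limit of 39.8%.

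**Working it through.** **Inputs from the documents.** 20 subjects (Source and sample size); 4 clinicians rating separately (Study Design – Overview); one-sided 95%, n=20, normal approximation, distance 0.18 (Sample Size Justification); threshold 80% (Endpoints).

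**Assumed.** Every clinician rates every video, giving 4 × 20 = 80 ratings per movement. The correlation ρ between one clinician's ratings of the same movement on different videos is not given, so it is varied from 0 to 1.

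**1. The plan's own figure.** Distance = 1.645 × √(p(1−p)/n). At p=0.5 and n=20 this is 1.645 × √(0.25/20) = 0.184, which matches 0.18. At p=0.8 it is 0.147. The arithmetic is right for 20 independent observations.

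**2. Effective sample size for usefulness.** Effective n = 80/(1+(20−1)ρ). Setting this equal to 20 gives 1+19ρ = 4, so ρ = 3/19 = 0.158. The third column puts effective n into the plan's formula at p=0.5. The fourth is the coverage of a nominal 95% exact interval with n=20, placed on the pooled rate rounded to 20ths. It was simulated from a beta-binomial model with a true rate of 80% and 40,000 runs.

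| ρ (assumed) | Effective n | Worst-case one-sided distance | Coverage, exact interval at n=20 |
|---|---|---|---|
| 0 | 80 | 0.092 | 100% |
| 0.05 | 41.0 | 0.128 | 99.9% |
| 0.158 | 20.0 | 0.184 | 98% |
| 0.3 | 11.9 | 0.238 | 92% |
| 0.5 | 7.6 | 0.298 | 80% |
| 0.7 | 5.6 | 0.348 | 66% |
| 0.9 | 4.4 | 0.391 | 49% |
| 1 | 4.0 | 0.411 | 41% |

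The last coverage figure is direct. With fixed opinions the pooled result can only be 0, 5, 10, 15 or 20 out of 20. Of the resulting intervals only that for 15/20 (50.9–91.3%) contains 80%, and three of four approvals have probability 4 × 0.8³ × 0.2 = 0.41.

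**3. Exact two-sided 95% intervals.** 20/20: 83.2–100%. 16/20: 56.3–94.3%. 4/4: 39.8–100%. 3/4: 19.4–99.4%. For illustration only, since the plan does not name a pooled analysis, 80/80 gives 95.5–100%.

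**4. If movements are the denominator.** The analysis sentence speaks of a rate of movements. Its n would then be the number of movements, which the available text does not give. Neither n=20 nor 0.18 would apply to that interval, and each movement's success would still rest on the same four clinicians.

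**5. The threshold.** If usefulness is counted as x of 4, then 3/4 = 75% fails and only 4/4 reaches 80%.

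**The case against.** The strongest reply is that the plan never specifies the intervals being criticised. It names n=20 only in the precision statement, never mentions 80 ratings, and words the analysis interval as a rate of movements. This stands in part: figures for 80 pooled ratings are illustrative, and the denominator is undefined. It does not rescue the 0.18. With movements as the denominator, n=20 is not the sample size. With subjects or ratings, independence fails.

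A second reply is that ρ is unknown. The clinician first identifies what is on each video, so a misidentified or poorly performed movement could change the second answer. This also stands. The wording makes a high ρ plausible but does not establish ρ=1. At ρ=0.2 effective n is 80/4.8 = 16.7 and the worst-case distance is 0.20, little different from 0.18. An exact n=20 interval still covers 98% at ρ=0.158 and drops below 95% only between there and 0.3.

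A reader might therefore infer that the planned error bars are far too narrow in general. The documents do not support that, because it depends on an assumed ρ and an unstated denominator. Nor do they support the inference that the success decision is invalid: no confidence limit is tied to the 80% criterion. Nor do they claim that the result extends to clinicians at large. If the four are a fixed panel, the result describes that panel, and the plan should say so.

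Finally, collecting only one usefulness answer per clinician would discard the data that could show how far answers vary between videos, and would turn the 80% criterion into unanimity without saying so. That is a fair objection to such a remedy, and the fix below avoids it.

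**Conclusion.** The concern holds in a limited form. The precision that justifies n=20 does not describe the usefulness judgement, because the same four clinicians repeat it over 20 videos and the plan makes no allowance for this. The size depends on ρ. By the effective-n formula the stated precision is too favourable once ρ exceeds about 0.16, and at ρ=1 the worst-case distance is 0.41 instead of 0.18. The effective-n figures assume that all four clinicians rate every video. The 0.41 uses the plan's own normal approximation at n=4 for a like-for-like comparison; it is not a recommended interval.

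The point concerns usefulness. Recognition can vary with the subject, so the 20 subjects do inform it, although those ratings too are repeated by the same four clinicians. Its weight also depends on whether usefulness is the primary endpoint, on which the synopsis endpoints and objectives differ.

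**What to change.** 1. In Sample Size Justification, state that n=20 and 0.18 apply to recognition of movements across subjects, with allowance for repeated ratings by the same clinician, and not to usefulness.
2. Keep the ratings as planned. For each movement, report usefulness by clinician: each clinician's rate over the videos, and how many of the four recommend the movement. Do not add a binomial interval that treats subjects or ratings as independent. Either cluster any interval by clinician or give the result descriptively.
3. In Study Hypothesis – Primary Endpoint, state the denominator and how the 80% criterion is applied across the four clinicians. If an x-of-4 rule is chosen, say that it requires 4/4.
4. Word the usefulness conclusion as agreement within this four-clinician panel.

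The cost is protocol and analysis-plan wording and a modest change to the tables. No subjects, raters or ratings are added. The downside is that the stated precision for usefulness becomes less favourable.

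### The 0.18 precision figure behind n=20 is for a one-sided normal interval, but the plan relies on exact intervals, which reach 0.21 (one-sided) or 0.24 (two-sided)

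*Combined protocol and SAP*

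**What the plan says.** All the relevant statistical text is in Statistical Considerations and Analysis.

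- **Sample Size Justification, first sentence:** "The rationale for the sample size is based on obtaining exact 95% confidence intervals for the activity movements which achieved 80% success". The method is exact; sidedness is not given.
- **Sample Size Justification, second sentence:** for a sample of 20, "a one-sided 95.0% confidence interval for a single proportion using the large sample normal approximation will extend at most 0.18 from the observed proportion". This is the only number offered in support of n=20.
- **Study Hypothesis – Primary Endpoint:** "The number and percentage of neck movements which achieve a success rate of at least 80% will be tabulated", followed by "Exact 95% binomial confidence intervals will be calculated for the rate of neck movements which achieve 80% success". The method is again exact; neither sidedness nor denominator is given.

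Two other places bear on the unit. Source and sample size says "Twenty (n=20) healthy adult subjects will be included in this study". The Overview under Study Design says "The video will be viewed and evaluated separately by 4 clinicians". The Endpoints section sets the acceptance criterion at 80% and does not link it to a confidence limit.

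**The concern.** The rationale and the analysis both name the exact method, while the number between them comes from the normal approximation. Exact (Clopper-Pearson) intervals are generally wider than normal ones at a sample of this size, so a bound worded as a maximum may fail for the interval that will actually be reported.

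Since 0.18 is the sole quantitative support for the sample size, the stated precision of the design depends on it. A reader would take an observed 80% to have a lower limit of at least 0.80 − 0.18 = 0.62.

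The unit is a second mismatch. The precision sentence uses a denominator of 20, which is the number of subjects. The analysis sentence puts the interval on a rate of movements, whose literal denominator is the number of movements. Unless this is settled, two analysts could report different primary intervals from the same data.

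**Working it through.** **Inputs.** n = 20, 95% confidence, one-sided, normal approximation, stated maximum 0.18 (Sample Size Justification); exact method (Sample Size Justification and Primary Endpoint analysis); 80% threshold and 4 clinicians per video (Study Design).

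**1. The plan's own figure.** The distance from a proportion p to a one-sided 95% normal limit is 1.645 × √(p(1−p)/n), largest at p = 0.5:

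1.645 × √(0.25/20) = 0.184.

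This reproduces the stated 0.18 to rounding. The two-sided normal figure, 1.960 × √(0.25/20) = 0.219, does not. So 0.18 is correct for the interval it names.

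**2. The exact method with 20 as denominator.** For x successes out of n, the Clopper-Pearson lower limit is the α quantile of Beta(x, n−x+1), and the upper limit is the 1−α quantile of Beta(x+1, n−x). Here α = 0.05 for a one-sided limit and 0.025 in each tail for a two-sided interval. The largest distance from x/20 to a limit, over all x, is:

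| Interval, n = 20 | Largest distance | Occurs at |
|---|---|---|
| Normal, one-sided (as stated) | 0.184 | p = 0.5 |
| Exact, one-sided lower | 0.208 | 13/20 |
| Exact, two-sided | 0.243 | 6/20 and 14/20 |

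The change of method accounts for 0.208 − 0.184 = 0.024, and two-sidedness for a further 0.243 − 0.208 = 0.035. The exact one-sided lower distance exceeds 0.184 at every count from 9 to 17 of 20.

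**3. At the 80% threshold (16/20).**

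- One-sided normal: 0.80 − 1.645 × √(0.16/20) = 0.80 − 0.147 = 0.653.
- Exact one-sided lower limit: 0.599, a distance of 0.201.
- Exact two-sided interval: 0.563 to 0.943, distances of 0.237 below and 0.143 above.

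**4. Size of the gap in subjects.** The largest exact distance first rounds to 0.18 at n = 25 one-sided (0.184) and n = 34 two-sided (0.182). This is a yardstick only, not a request for more subjects.

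**5. Other denominators.** The number of movements is not in the text available, so the counts of 4 to 12 below are assumptions for illustration.

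| Denominator | Exact one-sided lower, maximum | Exact two-sided, maximum |
|---|---|---|
| 4 movements | 0.527 | 0.602 |
| 6 movements | 0.415 | 0.475 |
| 8 movements | 0.350 | 0.402 |
| 10 movements | 0.307 | 0.356 |
| 12 movements | 0.277 | 0.322 |
| 20 subjects × 4 clinicians = 80 ratings, treated as independent | 0.098 | 0.116 |

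The last row is too optimistic: ratings of one video by several clinicians, and of several videos by one clinician, are not independent.

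**The case against.** The strongest reply is that the firm inconsistency is small. Like for like (one-sided, n = 20), 0.18 becomes 0.21. At 16/20 the implied lower limit moves only from 0.62 to 0.60, and at 18/20 or above 0.18 still holds to rounding. The plan states openly that its figure is a one-sided large-sample approximation. No decision turns on it, because the 80% criterion is not tied to a confidence limit.

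Most of this is true, and it limits the weight of the point. It does not remove the contradiction. The sentence just before the figure gives exact intervals as the basis for n, and a stated maximum that fails from 9/20 to 17/20, including at the study's own threshold, is not a maximum for the planned method.

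The second reply is that the plan nowhere says two-sided; the only sidedness it states is one-sided. That stands. The 0.24 rests on the usual reading of an unqualified 95% interval, so both figures are given here and the sponsor should choose.

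The third is that the movement list may have been lost from the available text, and that pooling 80 ratings as independent would make 0.18 too pessimistic rather than too optimistic. Both stand. The missing count is not held against the plan, and the direction of the error is established only for a denominator of 20. What remains, whatever the count, is that the two sentences use different units.

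**Conclusion.** The concern holds and should be fixed. The figure 0.18 is not an arithmetic error; it describes an interval that the plan neither rests on nor intends to report. With 20 as denominator, the exact method gives at most 0.21 one-sided (0.024 more than the plan's 0.184) or 0.24 two-sided (0.059 more, about a third). At 16/20 the exact lower limit is 0.60 or 0.56.

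These results assume Clopper-Pearson limits and one binary outcome per subject for each movement. If the unit is the movement, precision is poorer than this at any of the counts assumed (4 to 12). The correction changes the stated precision, not the sample size or the acceptance rule. The absence of a rule for combining the four clinicians' ratings is missing detail, and the conclusion does not depend on it.

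**What to change.** Keep n = 20 and make method, sidedness and unit agree in the two places.

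1. **Sample Size Justification.** Replace the 0.18 sentence with one of these:
   - *Two-sided:* With 20 subjects, an exact two-sided 95% CI for the success proportion of a given movement extends at most 0.24 from the observed proportion; at 16/20 it is 0.56 to 0.94.
   - *One-sided:* With 20 subjects, an exact one-sided 95% lower confidence limit for the success proportion of a given movement lies at most 0.21 below the observed proportion; at 16/20 it is 0.60.
2. **Primary Endpoint analysis.** If the unit is the subject within a movement: *For each movement, the proportion of the 20 subjects counted as a success, after combining the four clinicians' ratings by a rule stated in advance, will be given with an exact 95% binomial CI (sidedness as in the sample size section); the number and percentage of movements reaching at least 80% will be tabulated.*

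If the interval is meant for the rate of movements, state the number of movements and the exact precision at that number. If all ratings are to be pooled, use an interval that allows for clustering by video and by clinician.

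The text change is two sentences, with IRB approval of the amendment. It needs no extra subjects or data and leaves the 80% criterion alone. The real cost is that the sponsor must commit to a unit and a sidedness and, under the subject-level option, to a definition of success and a rule for combining ratings. The stated precision also becomes somewhat less favourable.

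### The 0.18 precision quoted for 20 subjects is a one-sided normal-approximation figure that does not bound the exact interval the plan promises, and the primary-analysis sentence leaves that interval's denominator open

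*Combined protocol and SAP*

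**What the plan says.** Under Sample Size Justification, the plan first names the target: "The rationale for the sample size is based on obtaining exact 95% confidence intervals for the activity movements which achieved 80% success". The figure offered in support belongs to another kind of interval: "When the sample size is 20, a one-sided 95.0% confidence interval for a single proportion using the large sample normal approximation". Of this second interval the plan states that it "will extend at most 0.18 from the observed proportion". The 20 are subjects, as the section on source and sample size states: "Twenty (n=20) healthy adult subjects will be included in this study".

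Under Study Hypothesis – Primary Endpoint, the plan tabulates the number and percentage of neck movements whose success rate is at least 80%. It continues: "Exact 95% binomial confidence intervals will be calculated for the rate of neck movements which achieve 80% success". It does not say whether this interval is one-sided or two-sided.

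The synopsis defines the primary endpoint as a count of movements: "Number of VRP-Clinic neck movements that the evaluator recognizes as useful for rehabilitation". The Overview of the Study Design adds the raters: "The video will be viewed and evaluated separately by 4 clinicians". The evaluation section refers to a list of movements, but the text available to this review does not show how many there are.

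**The concern.** There are two mismatches between the sizing statement and the planned analysis.

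- **Method and sidedness.** The rationale promises an exact interval, while the figure offered in support comes from a one-sided normal approximation. At n=20 the exact interval is wider, so the stated maximum may not hold for the interval that will be reported.
- **Denominator.** The interval sentence directly follows the tabulation of the percentage of movements reaching 80%. Read in that order, its rate is that percentage, and its denominator is the number of movements, M. Enrolling 20 subjects does not set the precision of such an interval. The binomial model is also doubtful for it, because the same subjects perform all the movements and the same four clinicians rate them.

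What is at stake is the reported precision of the primary result. Two analysts could follow the same text and produce different primary intervals: one over movements, the other per movement over subjects.

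**Working it through.** **Inputs.** From Sample Size Justification: n=20, one-sided 95%, normal approximation, maximum distance 0.18. From the endpoint definition: success criterion 80%. M is not in the available text, so values of M below are assumptions.

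**Step 1: the plan's own figure.** The distance is z × √(p(1−p)/n), largest at p=0.5. One-sided: 1.645 × 0.5/√20 = 0.184, which matches the stated 0.18. The two-sided counterpart is 1.960 × 0.5/√20 = 0.219.

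**Step 2: exact interval over 20 subjects.** The Clopper-Pearson lower limit for x successes is the α quantile of a Beta(x, n−x+1) distribution, with α=0.05 one-sided and α=0.025 two-sided. Distance from the estimate to the lower limit:

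| Outcome | One-sided 95% | Two-sided 95% |
|---|---|---|
| 13/20 | 0.208 (maximum) | 0.242 |
| 14/20 | 0.208 | 0.243 (maximum) |
| 16/20 (80%) | 0.201 | 0.237 |
| 18/20 | 0.183 | 0.217 |
| 19/20 | 0.166 | 0.199 |
| 20/20 | 0.139 | 0.168 |

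Among outcomes of 80% or more, the exact distance is below 0.18 only at 19/20 and 20/20 one-sided, and only at 20/20 two-sided.

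**Step 3: separating method from sidedness.**
- Method, one-sided: 0.208 − 0.184 = 0.024.
- Method, two-sided: 0.243 − 0.219 = 0.024.
- Sidedness, normal approximation: 0.219 − 0.184 = 0.035.

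So of the full difference of 0.243 − 0.184 = 0.059, about 0.024 comes from the method and 0.035 from sidedness.

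**Step 4: literal reading, denominator M (assumed).** The same exact one-sided calculation, maximised over outcomes:

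| M | Maximum distance to the lower limit |
|---|---|
| 4 | 0.527 |
| 10 | 0.307 |
| 20 | 0.208 |
| 30 | 0.166 |

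These values treat movements as independent. The effect of dependence is not computed, because it needs M and a correlation that the documents do not give.

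**The case against.** The strongest defence is that 0.18 is correct as labelled. The sentence says it is one-sided and uses the normal approximation, and it never calls 0.18 the exact precision. That stands: the arithmetic is not in error. What fails is its use as support for a rationale stated in terms of exact intervals.

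It can also be said that the effect is small. On the reading that fits n=20, matched for sidedness, the difference is 0.024, and near 100% success the exact distance is below 0.18. This stands too, and it limits the point to the claimed maximum.

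On the denominator, the rationale sentence speaks of intervals in the plural for the movements, which supports one interval per movement over 20 subjects. So the wording is ambiguous, and a wrong denominator is not established. Nor is the missing value of M a fault in the plan: the list that the evaluation section refers to may not have survived text extraction. If M were 30, 0.18 would not understate even the literal one-sided exact interval under independence (0.166).

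A reader might also infer that the four clinicians' ratings will be pooled into 20 × 4 = 80 observations per movement, giving falsely narrow intervals. The plan describes no such pooling. It gives no combining rule, so the fix only needs to close off that route.

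**Conclusion.** The point holds in two limited parts.

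First, 0.18 is not the maximum for an exact interval over 20 subjects. That maximum is 0.208 one-sided or 0.243 two-sided, and the distance is 0.201 or 0.237 at 16/20. The plan does not say which side applies. This part needs no outside assumption beyond taking exact to mean Clopper-Pearson.

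Second, the primary-analysis sentence read literally has M as its denominator, with movements that are not independent. Its size depends on M and cannot be fixed from the documents.

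A reader might infer that the study is too small. The exact maximum would indeed come down to about 0.18 only at a denominator of about 26 one-sided or 35 two-sided. But the plan sets no required precision that 20 subjects then miss; it only reports what 20 subjects give. A reader might equally infer that the success decision is compromised. The documents do not tie the interval to the 80% criterion, so pass or fail is unaffected. The matter should be corrected because it concerns how the primary result is reported, but it does not threaten the study's conclusion.

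**What to change.** 1. In Sample Size Justification, replace the 0.18 statement with the figure for the exact interval that will be reported: at most 0.21 (one-sided) or 0.24 (two-sided) below the observed proportion. State which applies, and use the same sidedness in the primary analysis.
2. In Study Hypothesis – Primary Endpoint, report the number and percentage of movements reaching 80% descriptively. Attach the exact interval to each movement's success proportion on the primary endpoint over the 20 subjects. Do this either by clinician or under one combining rule fixed before the videos are read. Do not treat the four clinicians' ratings of the same video as independent, and describe the intervals as conditional on these four clinicians.

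The cost is wording and a few more tables, with no new data and no more subjects. The downside is a slightly less favourable stated precision and no interval on the headline count of movements.
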